- 5) Ineligibility due to a known protocol violation, change of pathology diagnosis after enrolment, etc.
- 6) The principal investigator or a member of research team decides that continuation of treatment is not appropriate, taking into account efficacy or safety.

If this protocol treatment is discontinued, follow the decision of the attending doctor with regard to subsequent treatment. The reasons for discontinuation should be documented in the medical record and the case report form. If consent is withdrawn after treatment has started, it should be made as clear as possible whether the withdrawal of consent was due to ineffectiveness of the treatment or to an adverse or incidental event, and this should be record in order to assist in the selection of the case for safety evaluation. If circumstances permit, a discontinuation inspection should be carried out within 14 days of the decision to discontinue (see 2.7.).

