- 5) Blood biochemistry: total protein, albumin, total bilirubin, direct bilirubin, AST, ALT, ALP, γ -GTP, BUN, creatinine, LDH, uric acid, CPK, P, Ca, Na, K, Cl, CRP, blood glucose.
- 6) Presence of adverse events (CTCAE v4.0 Japanese translation).
- 7) Immunological parameters.

During nivolumab administration

(After the second dose, assess the following items on the day of administration or the day before administration. Assess following items once from 7 days before to 7 days after the imaging examination date.)

- 1) General findings (temperature, blood pressure, pulse).
- 2) General condition: PS (ECOG).
- 3) Subjective and objective symptoms: fever, nausea, vomiting, diarrhea, decreased appetite, etc. (to be confirmed according to CTCAE v4.0 Japanese translation).
- 4) Blood count (peripheral blood): white blood cell count and fractions, red blood cell count, hemoglobin, MCV, MCH, MCHC, Ht, platelets.
- 5) Blood biochemistry: total protein, albumin, total bilirubin, direct bilirubin, AST, ALT, ALP, γ -GTP, BUN, creatinine, LDH, uric acid, CPK, P, Ca, Na, K, Cl, CRP, blood sugar.
(The following items are only available at the third and sixth doses) RA, ANA, SP-D, KL-6, TSH, free T3, free T4, tumor markers (CEA, CA19-9).
- 6) Contrast-enhanced CT of the chest, abdomen and pelvis (at third and sixth doses). PET-CT is also acceptable. Add MRI if necessary.
- 7) Presence or absence of PD (diagnosed comprehensively based on imaging and clinical findings).
- 8) Presence or absence of adverse events (CTCAE v4.0 Japanese translation).
- 9) Immunological parameters.

During observation

(Assess following items once from 14 days before to 14 days after the 3rd and 6th dose of Nivolumab and Day120.)

- 1) Contrast-enhanced CT of chest, abdomen and pelvis. PET-CT is also acceptable. Add MRI if necessary.

After completion of the protocol

(Assess following items once from 14 days before to 14 days after the Day180.)

- 1) General findings (temperature, blood pressure, pulse).
- 2) General condition: PS (ECOG).
- 3) Subjective and objective symptoms: fever, nausea, vomiting, diarrhea, decreased appetite, etc. (to be confirmed according to CTCAE v4.0 Japanese translation).
- 4) Blood count (peripheral blood): white blood cell count and fractions, red blood cell count, hemoglobin, MCV, MCH, MCHC, Ht, platelets.

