- 5) Blood biochemistry: total protein, albumin, total bilirubin, direct bilirubin, AST, ALT, ALP, γ -GTP, BUN, creatinine, LDH, uric acid, CPK, P, Ca, Na, K, Cl, CRP, blood sugar, RA, ANA, SP-D, KL-6, TSH, free T3, free T4, tumor markers (CEA, CA19-9).

- 6) Contrast-enhanced CT of chest, abdomen and pelvis. PET-CT is also acceptable. Add MRI if necessary.
- 7) Presence or absence of PD (diagnosed comprehensively based on imaging and clinical findings).
- 8) Presence or absence of adverse events (CTCAE v4.0 Japanese translation).
- 9) Immunological parameters.

At the time of cessation of treatment

(Assess following items once within 14 days after the decision to discontinue. Assessment of following items within 14 days prior to the date of cessation of treatment is valid. If the subject is dead, hospitalized in another hospital, or otherwise unable to come to the hospital, these situations should be noted).

- 1) General findings (temperature, blood pressure, pulse).
- 2) General condition: PS (ECOG).
- 3) Subjective and objective symptoms: fever, nausea, vomiting, diarrhea, decreased appetite, etc. (to be confirmed according to CTCAE v4.0 Japanese translation).
- 4) Blood count (peripheral blood): white blood cell count and fractions, red blood cell count, hemoglobin, MCV, MCH, MCHC, Ht, platelets.
- 5) Blood biochemistry: total protein, albumin, total bilirubin, direct bilirubin, AST, ALT, ALP, γ -GTP, BUN, creatinine, LDH, uric acid, CPK, P, Ca, Na, K, Cl, CRP, blood sugar, RA, ANA, SP-D, KL-6, TSH, free T3, free T4, tumor markers (CEA, CA19-9).
- 6) Contrast-enhanced CT of chest, abdomen and pelvis. PET-CT is also acceptable. Add MRI if necessary.
- 7) Presence or absence of PD (judged comprehensively based on imaging and clinical findings).
- 8) Presence or absence of adverse events (CTCAE v4.0 Japanese translation).
- 9) Immunological parameters.

Inspection schedule

| | | | | | | | | | |
|---|---|---|---|---|---|---|---|---|---|
| Period | | | | | | | | | |
| Patient background | ○ | | | | | | | | |
| General findings | ○ | ○ | | | | | | | |
| General condition | ○ | ○ | ○ | | | | | | |
| Subjective and objective symptoms | ○ | ○ | ○ | ○ | | | | | |
| Imaging | ○ | | | | ○ | | | | |
| ECG | ○ | | | | | | | | |
| Blood count | ○ | | ○ | ○ | ○ | ○ | ○ | ○ | ○ |
| Coagulation | ○ | | | | | | | | |
| Blood biochemistry | ○ | | ○ | ○ | ○ | ○ | ○ | ○ | ○ |
| Urinalysis | ○ | | | | | | | | |
| Infection | ○ | | | | | | | | |

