6.5 Sensitivity analysis (handling of omissions or missing values)

Not conducted in this study.

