7.2 Investigation of clinical laboratory values

1) Purpose

Examine the clinical laboratory values to examine the safety of protocol treatment.

5) Analysis population

FAS.

2) **Analysis items**

Vital signs (temperature, pulse, blood pressure).

Subjective and objective findings (PS, fever, nausea, vomiting, diarrhea, decreased appetite).

Hematological examination (white blood cell count, neutrophil ratio, lymphocyte ratio, monocyte ratio, eosinophil ratio, basophil ratio, red blood cell count, hemoglobin concentration, MCV, MCH, MCHC, Ht, platelets).

Blood biochemical tests (total protein, albumin, total bilirubin, direct bilirubin, AST, ALT, γ -GTP, BUN, creatinine, LDH, uric acid, CPK, P, Ca, Na, K, Cl, CRP, blood sugar, rheumatoid factor (RF), anti-nuclear antibodies (ANA), SP-D, KL-6, thyroid-stimulating hormone (TSH), free triiodothyronine (free T3), free thyroxine (free T4), CEA, CA19-9).

3) **Analysis methods**

Prepare transition graphs (per individual and group) of the measured values. Calculate the basic statistics (median and quartiles, or frequency and rate) of the measured values.

Prepare lists of vital signs, subjective and objective findings, hematological examination, and blood biochemistry tests.

8. List of patient data

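### SAP 7.2 summarises group laboratory trends as raw values, so later dose-visit points rest on a selected, fitter subset and can look stable or better with no change within patients

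*SAP*

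**What the plan says.** SAP 7.2 has a safety purpose: "Examine the clinical laboratory values to examine the safety of protocol treatment". Its population is the FAS. The methods are "Prepare transition graphs (per individual and group) of the measured values" and "Calculate the basic statistics (median and quartiles, or frequency and rate) of the measured values", plus lists. It names no change from baseline, no count per time point, no definition of the time axis, and no place for a value taken when treatment stops.

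The protocol decides who is tested and when:

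- **On treatment (2.7).** "After the second dose, assess the following items on the day of administration or the day before administration". CRP and LDH are in the panel for every dose. For RA, ANA, SP-D, KL-6, thyroid tests, CEA and CA19-9, "The following items are only available at the third and sixth doses".
- **At cessation (2.7).** A full panel including LDH, CRP, CEA and CA19-9: "Assess following items once within 14 days after the decision to discontinue". Values from the 14 days before cessation also count. Section 2.5 makes it conditional: "If circumstances permit, a discontinuation inspection should be carried out within 14 days of the decision to discontinue". Section 2.7 accepts that patients who have died, are in another hospital or cannot attend may not have it.
- **Day 180 ± 14 (2.7).** One full panel, placed under the heading for the period after protocol completion. Whether patients who stopped early have it is not stated.
- **Reasons to stop nivolumab (2.5).** They include clinical worsening from progression, Grade 3 or higher thrombocytopenia, stated AST/ALT and bilirubin elevations, and failing the dosing conditions of 2.3(2) without resuming within 14 days. Those conditions cover white cells, neutrophils, hemoglobin, platelets, bilirubin, AST/ALT and creatinine.

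**The concern.** A median of raw values at successive dose visits mixes two things: change within patients, and change in who is measured. Here the second is not random. Patients leave the dose-visit series because their disease worsens or, for the dosing-condition tests, because the plotted value itself has deteriorated. The group curve can then look flat or improved on the parameters that 7.2 is meant to monitor, although nobody has improved. For hemoglobin, platelets and white cells the misleading direction is upward; for CRP, LDH, liver tests and tumor markers it is downward.

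The markers taken only at the third and sixth doses have just two on-treatment points, so their group trend depends heavily on who is left at dose six. At stake is how fairly a descriptive safety figure reads.

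**Working it through.** The documents give no figure for laboratory trends or for attrition, so there is no stated result to reproduce. The check asks how far the raw group median can move when no patient changes.

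**Inputs from the documents.** 40 patients (protocol 2.8). Section 2.8 also gives an indirect guide to attrition: disease control of 40% (reference) to 60% (hoped for) leaves 100 − 60 = 40% to 100 − 40 = 60% without control. Not all of these need stop before dose six, and patients also stop for other reasons.

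**Assumed inputs.** Share gone, 20%, 40% or 60%. Correlation r between the baseline marker and the tendency to leave, 0, 0.3 or 0.5. Log-normal marker with log-SD 0.5, 1.0 or 1.5. Each patient's value is constant over time.

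**Step 1, closed form (large sample).** If a share s stays, and z cuts off that share of a standard normal, the mean log marker of those staying shifts by −r × φ(z)/s SD. The median shifts by about the same.

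- Mildest case: s = 0.8, φ(0.842)/0.8 = 0.280/0.8 = 0.350. Times r = 0.3 gives 0.105 SD. At log-SD 0.5, 1 − exp(−0.0525) = 5%.
- Strongest case: s = 0.4, φ(0.253)/0.4 = 0.386/0.4 = 0.966. Times r = 0.5 gives 0.483 SD. At log-SD 1.5, 1 − exp(−0.724) = 52%.

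**Step 2, simulation at the trial's size.** 3,000 trials of 40 patients, keeping 32, 24 or 16. The table gives the apparent fall in the raw group median relative to baseline (median over trials).

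| Share gone | r | log-SD 0.5 | log-SD 1.0 | log-SD 1.5 |
|---|---|---|---|---|
| 20% | 0.3 | 4.2% | 8.2% | 11.5% |
| 20% | 0.5 | 7.0% | 13.8% | 20.3% |
| 40% | 0.3 | 8.0% | 14.9% | 21.8% |
| 40% | 0.5 | 13.8% | 25.4% | 35.7% |
| 60% | 0.3 | 12.1% | 23.0% | 31.3% |
| 60% | 0.5 | 20.1% | 35.4% | 49.0% |
| any | 0 | 0% | 0% | 0% |

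The median within-patient ratio to baseline stays at 1 throughout, as it must when the marker is held constant.

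**Step 3, leavers deteriorate.** Now let each leaver's value rise 30% by the cessation test.

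- The raw median of those still tested still falls by 4–48% at r = 0.3–0.5.
- The paired change in those still tested is still 0%, so it misses the deterioration too.
- The median of every patient's last value rises by about 2–5% with 20% gone, 10–11% with 40% gone and 17–19% with 60% gone.

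Paired change therefore removes the false improvement, but only a summary that includes the leavers' last values shows the worsening.

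**The case against.** The strongest reply is that little rests on this curve, and most of that reply stands. The same sentence of SAP 7.2 plans individual graphs, and 8.9 lists values for each patient. SAP 7.1 tabulates adverse events by worst grade from the start of radiotherapy, and protocol 6.1 has Grade 3 or higher events recorded to Day 180 whether or not related. CEA, CA19-9, CRP and LDH are not efficacy endpoints, and no test uses the group graph.

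A reader might infer three stronger things, which the documents do not support:

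- *Laboratory testing ends when treatment stops.* It does not. Dose-visit testing ends. A cessation panel follows if circumstances permit, and there is a Day 180 panel. The gap is that the SAP gives the cessation value no place in the group summary, that the sickest patients are the likeliest to miss it, and that Day 180 coverage of early stoppers is unstated.
- *SAP 6.5 rules out handling missing laboratory values.* Section 6.5 belongs to the efficacy chapter. Section 7.2 is simply silent.
- *A tumor marker would falsely fall by up to about half.* That is the extreme corner of assumed inputs. Patients also stop for toxicity or at their own request, so the correlation may be weak for some markers, and at zero there is no shift.

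It is also fair to say that change from baseline among those still tested remains a survivor summary. Step 3 confirms this, so paired change alone is not a complete remedy.

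**Conclusion.** The point holds as a minor improvement to a descriptive safety display. SAP 7.2 summarises the group only through raw values, while dose-visit testing depends on continuing nivolumab, and the protocol ties stopping to progression and to several of the plotted results. Later group points can therefore look stable or better with no improvement in any patient.

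The size cannot be derived from the documents. The 4–49% range rests wholly on assumed attrition, correlation and marker spread, and it describes selection on baseline values only. For the dosing-condition tests the selection is on the current value; the protocol establishes that link but not its strength. Individual graphs, listings and worst-grade tables let a careful reader detect the problem, though they do not correct the group medians. The primary endpoint, its confidence interval and survival are unaffected.

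**What to change.** In SAP 7.2:

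1. At each time point, report the number measured, the within-patient change (or ratio) from baseline, and the baseline median of the same patients.
2. Show the cessation value separately as an end-of-treatment value. It can be taken up to 14 days after the decision to stop, so it should not be plotted as an on-treatment visit.
3. Add last-value and worst-value summaries for every treated patient with a post-baseline value. State how many have none.
4. State which patients contribute to the Day 180 point, and have protocol 2.7 say whether early stoppers have that panel.
5. Keep the individual graphs and lists.

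The cost is a few lines of SAP wording, a clarifying sentence in the protocol, and somewhat more programming and tables. Items 1–3 use data already collected under the plan.

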8.1 List of cases excluded from safety analysis (untreated cases)

1) **Purpose**

Prepare a list of untreated cases.

2) **Analysis object**

Untreated cases

3) **Analysis items**

Case number, institution name, age, gender, reason for not treated.

8.2 List of cases excluded from efficacy analysis

1) **Purpose**

Prepare a list of cases excluded from FAS.

2) **Analysis object**

Cases excluded from FAS.

3) **Analysis items**

Case number, institution name, age, gender, reason for exclusion from analysis.

8.3 List of early discontinuation cases

1) **Purpose**

Prepare a list of early discontinuation cases.

4) **Analysis object**

Safety analysis population.

2) **Analysis items**

Case number, institution name, age, gender, date of discontinuation, reason for discontinuation.

8.4 List of cases of deviation from the Study Protocol

1) **Purpose**

Prepare a list of cases of deviation from the Study Protocol.

2) **Analysis object**

Cases of deviation from the Study Protocol.

3) **Analysis items**

Case number, institution name, age, gender, reason and extent of the deviation.

8.5 Lists regarding demographic data/baselines

1) **Purpose**

Prepare a list of enrolled cases.

2) **Analysis object**

All enrolled cases.

3) **Analysis items**

Case number, institution name, age, gender, allergies, smoking cessation history, alcohol consumption history, medical history, complications, history of cancer chemotherapy, PS, RA, ANA, SP-D, KL-6, TSH, free T3, free T4, CEA, CA19-9.

8.6 List of treatment status

1) **Purpose**

Prepare a list of treatment status for cases subjected to safety analysis.

2) **Analysis object**

Safety analysis population.

3) **Analysis items**

Case number, age, gender, radiotherapy start date, radiotherapy end date, nivolumab administration date, concomitant medications.

8.7 List of effective response data

1) **Purpose**

Prepare a list of effective response data for cases subject to efficacy analysis.

2) **Analysis object**

FAS.

3) **Analysis items**

Case number, age, gender, radiotherapy start date, date of death or last verified survival, alive or dead status, regimen, irradiation site, best overall response on disease control, best overall response on local control, and changes in lesions over time (examination date, tumor diameter).

8.8 List of adverse events per patient

1) **Purpose**

Prepare a list of adverse events in cases in which adverse events are observed among the cases subjected to safety analysis.

2) **Analysis object**

Safety analysis population.

3) **Analysis items**

Case number, age, gender, name of adverse event (serious adverse events are marked with *), date of occurrence (day), worst grade, severity, outcome, date of outcome (day), relevance.

8.9 List of individual laboratory values and other information for each patient

1) **Purpose**

Prepare a list of laboratory values for cases in which vital signs, subjective and objective findings, and laboratory tests were performed.

2) **Analysis object**

Safety analysis population.

3) **Analysis items**

Vital signs (temperature, pulse, blood pressure).

Subjective and objective findings (PS, fever, nausea, vomiting, diarrhea, decreased appetite).

Hematological examination (white blood cell count, neutrophil ratio, lymphocyte ratio, monocyte ratio, eosinophil ratio, basophil ratio, red blood cell count, hemoglobin concentration, MCV, MCH, MCHC, Ht, platelets).

Blood biochemistry tests (total protein, albumin, total bilirubin, direct bilirubin, AST, ALT, γ -GTP, BUN, creatinine, LDH, uric acid, CPK, P, Ca, Na, K, Cl, CRP, blood glucose, rheumatoid factor (RF), antinuclear antibody (ANA), SP-D, KL-6, thyroid stimulating hormone (TSH), free triiodothyronine (free T3), free thyroxine (free T4), CEA, CA19-9).
